2.1.2.18 History of leptomeningeal carcinomatosis

2.1.2.19 Receipt of live attenuated vaccination within 30 days prior to the first dose of Vicineum or durvalumab

2.1.2.20 Any condition that, in the opinion of the investigator, would interfere with evaluation of study treatment or interpretation of patient safety or study results

2.1.2.21 Subjects with uncontrolled seizures

2.1.2.22 Any unresolved toxicity NCI CTCAE Grade  $\geq 2$  from previous anticancer therapy with the exception of alopecia, vitiligo, and the laboratory values defined in the inclusion criteria

- Subjects with Grade  $\geq 2$  neuropathy will be evaluated on a case-by-case basis after consultation with the Principal Investigator.  
Subjects with irreversible toxicity not reasonably expected to be exacerbated by treatment with durvalumab may be included only after consultation with the Principal Investigator.

### **2.1.3 Recruitment Strategies**

This study will be posted on NIH websites and on NIH social media forums. Additionally, this study will be listed on available websites ([www.clinicaltrials.gov](http://www.clinicaltrials.gov) and others) and participants will be recruited from the current patient population at NIH.

## **2.2 SCREENING EVALUATION**

Note: Screening evaluation testing/procedures are conducted under the separate screening protocol, 01-C-0129 (Eligibility Screening and Tissue Procurement for the NIH Intramural Research Program Clinical Protocols). Assessments performed at outside facilities or on another NIH protocol within the timeframes below may also be used to determine eligibility once a participant has signed the consent.

Evaluations to be performed within 12 weeks prior to starting treatment:

- History and physical examination (including medications, medical history, surgical history, previous treatments for bladder cancer with dates, allergies, and demography)
- ECOG performance status
- Formal review of available previous bladder tumor specimens by the Laboratory of Pathology, NCI, to confirm the bladder cancer diagnosis prior to enrollment into the study.
  - If outside bladder tumor specimens are inadequate to accurately stage the patient's disease, then additional biopsies will be performed at the NCI as part of standard of care therapy. Tissues obtained at the NCI will be used to confirm diagnosis and for study of immune-related markers. With preoperative patient permission, extra tissue not sent to Laboratory of Pathology, NCI, will be frozen for future analysis of immune-related markers and tumor infiltrates. This additional harvested tissue will be used for research purposes only and is not required for a candidate to participate in this protocol.
  - If outside bladder tumor specimens are adequate to accurately stage the patient's disease, cystoscopy with or without biopsy and/or TURBT to confirm diagnosis and resect and remove any residual papillary disease and fulgurate any CIS may be performed as part of standard of care therapy. With preoperative patient permission, extra tissue not sent to the Laboratory of Pathology, NCI, will be frozen for the future analysis of immune-related markers and tumor infiltrates. This additional harvested tissue will be used for research purposes only and is not required for a candidate to participate in this protocol. Blue light cystoscopy can be performed at urologist's discretion.
- Laboratory studies
  - Hematology (Complete blood count plus differential and platelet count)
  - Serum chemistries and liver function tests (Na+, K+, Cl-, CO2, glucose, BUN, creatinine, albumin, calcium, magnesium, phosphorus, alkaline phosphatase, ALT, AST, total bilirubin, LDH, pre-albumin, amylase, lipase)
  - Coagulation parameters (PT, PTT)

- Viral Studies (Hepatitis B and C; HIV)
- Thyroid function tests
- Urinalysis
- 24 hour urine (only if CrCL will not be calculated)
- PPD if indicated
- Computerized Tomography (CT) urogram or Magnetic Resonance Imaging (MRI) urogram. If urogram protocol not available or contrast allergy/poor renal function preclude such imaging, then CT or MRI of the abdomen/pelvis without contrast will suffice and investigator may perform retrograde pyelogram at their discretion.
- Electrocardiogram (ECG) for QT interval – Mean QT interval corrected for heart rate using Fridericia's formula (QTcF) will be calculated from a single ECG. If QTcF  $\geq$  470ms, then the patient must be excluded from trial.
  - Resting 12-lead ECGs will be recorded according to the assessment schedule. ECGs should be obtained after the patient has been in a supine position for 5 minutes and should be recorded while the patient remains in that position.
  - ECG will be recorded at Screening, in Week 2 (pre-durvalumab treatment) and as clinically indicated.
  - In case of clinically significant ECG abnormalities, including a QTcF value  $>470$  ms, 2 additional 12-lead ECGs should be obtained over a brief period (e.g., 30 minutes and at least 5 minutes apart) to confirm prolongation
- Serum or urine beta-HCG for women of child-bearing age

See section **3.4, Study Calendar** for more details.

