#### **VB4-845-02-IIA**

A Phase 2 study (VB4-845-02-IIA) evaluated once-weekly instillations of Vicineum 30 mg in two different induction schedules: weekly x 6 weeks or weekly x 12 weeks, followed by up to 3 maintenance cycles (3 once-weekly instillations followed by a 9-week drug-free period) in 46 subjects with histologically-confirmed TCC of the bladder and residual CIS with or without concurrent Ta or T1 who were refractory or intolerant to BCG. Some subjects in the 6-weekly induction arm received a second induction cycle. Forty-six subjects were considered evaluable for response. A complete response (defined as no histological evidence of disease and negative urine cytology at the 3-monthly evaluations) was achieved by 44% (20/45) of subjects, and 16% (7/45) of subjects remained disease-free at the 1-year end-of-study (EOS) assessment. A post-study assessment found that these subjects were still disease-free at 18-25 months. The median time to recurrence was 134 days longer in subjects who received 12 weeks of induction therapy compared to 6 weeks (408 vs 274 days, respectively; log rank test p=0.1708). The most frequently reported treatment-related AEs were renal and urinary disorders, including 50% with dysuria (61% of these were of mild intensity) and 13% with hematuria. Overall, most AEs were of mild severity. There were 3 severe events, all of which resolved without sequelae. No subject discontinued from the study due to AEs and there were no deaths or other serious AEs.

Based on the preliminary positive therapeutic results and favorable tolerability profile, the present Phase 3 trial will evaluate the efficacy of Vicineum induction therapy administered for 12 weeks, and the long-term effectiveness of Vicineum maintenance therapy (up to 24 months treatment in total) in preventing disease recurrence.

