## **2 ELIGIBILITY ASSESSMENT AND ENROLLMENT**

### **2.1 ELIGIBILITY CRITERIA**

#### **2.1.1 Inclusion Criteria**

2.1.1.1 Patients must have histologically or cytologically confirmed by NCI Laboratory of Pathology as high grade non-muscle invasive urothelial (transitional cell carcinoma) of the bladder as follows:

- Carcinoma-in-situ (CIS) with or without papillary tumors

- High-grade Ta or T1 disease based on a biopsy/TURBT performed within 12 weeks of the initial dose of study treatment. If multiple bladder biopsies/TURBTs are required to confirm eligibility, the timing of the last bladder biopsy to the initial dose of study treatment must be within 12 weeks.
- Patients with persistent T1 high grade disease on TURBT following a single induction course of BCG (at least 5 of 6 doses) may also be eligible for this trial provided that the patient is surgically unfit for cystectomy as deemed by the investigator or the patient declines cystectomy.

2.1.1.2 Subjects with BCG unresponsive disease as defined by the Society of Urologic Oncology and the FDA: Subjects must have received at least two courses of intravesical BCG (at least 5 of 6 induction doses of BCG and at least 2 of 3 maintenance doses of BCG under a maintenance regimen or at least 2 doses of a repeat induction course). Please note exception above for persistent T1 disease. There is no upper limit on the amount of prior BCG a subject may have received.

2.1.1.3 Patients who have met eligibility criterion **2.1.1.2** must have received last BCG dose within a year of enrollment.

2.1.1.4 The investigator must document that he/she believes the subject would not benefit from additional BCG treatment at the time of study entry.

2.1.1.5 Age  $\geq$  18 years at time of signing the informed consent form (ICF). Because no dosing or adverse event data are currently available on the use of Vicineum in combination with durvalumab in patients  $<18$  years of age, children are excluded from this study, but will be eligible for future pediatric trials. Furthermore, NMIBC does not occur in children.

2.1.1.6 Eastern Cooperative Oncology Group (ECOG) performance status 0 or 1 ( [Appendix A](#) )

2.1.1.7 Adequate organ and marrow function as defined below:

- Hemoglobin  $\geq$  9.0 g/dL
- Absolute neutrophil count (ANC)  $\geq$  1.5  $\times$  10^9/L ( $> 1500$  per mm^3)
- Platelet count  $\geq$  75  $\times$  10^9/L ( $>75,000$  per mm^3)

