##### **6.2.4.2 Complete Response Rate for CIS**

In patients with any component of CIS upon study entry, the complete response (CR) rate will be determined at 3 months, 6 months, and 12 months from the start of Vicineum therapy. Complete response will be defined as the absence of CIS upon follow-up biopsies. These rates can be compared to historical rates of CR for CIS at these various time points.

**Abbreviated Title:** Durvalumab & Vicineum for NMIBC

**Version Date:** 05/22/2025

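### CIS may be fulgurated before the first dose without residual CIS being required, so the complete response rate pools ablated and residual CIS and could be biased upward against residual-CIS series

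*Combined protocol and SAP*

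**What the plan says.** Entry. Section 2.1.1.1 admits patients with "Carcinoma-in-situ (CIS) with or without papillary tumors". The timing rule, written under the Ta/T1 item, is that "the timing of the last bladder biopsy to the initial dose of study treatment must be within 12 weeks". It limits the age of the last biopsy and does not ask that CIS remain after it.

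Between diagnosis and first dose. Where outside specimens are adequate for staging, section 2.2 allows a cystoscopy, with or without biopsy and/or TURBT, to "resect and remove any residual papillary disease and fulgurate any CIS may be performed as part of standard of care therapy". The procedure is optional.

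Evaluability. Section 6.2.4 requires disease proven on biopsy at baseline, at least one dose of each drug, and a re-evaluation. It does not say whether disease must persist after a pre-treatment procedure.

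Response. For patients with any CIS at entry, section 6.2.4.2 has CR "determined at 3 months, 6 months, and 12 months from the start of Vicineum therapy". It adds: "Complete response will be defined as the absence of CIS upon follow-up biopsies". On comparison it says: "These rates can be compared to historical rates of CR for CIS at these various time points". No series is named. Section 6.2.3 leaves biopsy to the investigator's discretion.

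Analysis. Section 10.4.3 reports one response rate with a two-sided 95% confidence interval, without a test or null rate. Section 10.4.7 plans no subgroup analyses.

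Background. The phase 2 study VB4-845-02-IIA (section 1.2.2.2) enrolled patients with "histologically-confirmed TCC of the bladder and residual CIS with or without concurrent Ta or T1". Its CR was "defined as no histological evidence of disease and negative urine cytology at the 3-monthly evaluations".

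**The concern.** CR should show that disease present when treatment began has gone. Here the CIS that qualifies a patient may be destroyed before the first instillation, and the later finding of no CIS is still credited as response. Because ablated and residual CIS are pooled, the reported rate mixes the effect of the procedure with that of the drugs, and nothing in the planned output lets a reader separate them.

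This matters mainly for the historical comparison. If the comparator enrolled CIS that was still present, fulguration before dosing can only raise this trial's rate relative to it. A modest apparent gain could then be read as added activity of the combination.

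**Working it through.** **1. Does anything restore a residual-CIS requirement?** The timing rule in 2.1.1.1 and the evaluability rule in 6.2.4 are the candidates. A specimen taken before or at fulguration can satisfy both. Section 5.1.3 treats the diagnostic biopsy, including one taken at an outside institution, as the baseline tissue, which supports that reading. The calendar in 3.4 lists cystoscopy at screening and then every 3 months, so no scheduled look after fulguration and before dosing would show what remained. No requirement was found.

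**2. The historical figure.** Phase 2 CR: 20/45 = 44.4%, matching the stated 44%. Exact (Clopper-Pearson) 95% interval: 29.6% to 60.0%. The same paragraph gives 46 evaluable subjects; 20/46 = 43.5%, which changes nothing here.

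**3. CR rate with no drug effect.** Three quantities are needed. None is in the documents, so all are assumptions:

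- f: share of CIS patients fulgurated before dosing (0 to 1);
- q: probability that fulgurated CIS is gone and still absent at 3 months without active drug (0.10 to 0.40);
- m: probability that one biopsy session misses CIS that is present (0 to 0.20).

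With c = f × q, the no-effect rate is CR0 = c + (1 − c) × m. The part due to fulguration alone is CR0 − m = c × (1 − m).

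| f | q | m | c | CR0 | due to fulguration |
|---|---|---|---|---|---|
| 0 | any | 0 | 0% | 0% | 0% |
| 0 | any | 0.10 | 0% | 10.0% | 0% |
| 0.25 | 0.10 | 0 | 2.5% | 2.5% | 2.5% |
| 0.50 | 0.20 | 0.10 | 10% | 19.0% | 9.0% |
| 0.50 | 0.40 | 0.10 | 20% | 28.0% | 18.0% |
| 1.00 | 0.40 | 0.20 | 40% | 52.0% | 32.0% |

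The last row is an extreme: every CIS patient fulgurated, at the top of the assumed clearance and miss ranges.

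**4. Effect on a comparison with 44%.** Suppose patients not cleared by fulguration respond at the phase 2 rate, so the combination adds nothing. Observed CR = c + (1 − c) × 0.44; m is left out because 0.44 already reflects that study's own sampling.

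- c = 10%: 0.10 + 0.90 × 0.44 = 49.6%, an apparent gain of 5.6 points.
- c = 20%: 0.20 + 0.80 × 0.44 = 55.2%, an apparent gain of 11.2 points.
- c = 0: no gain. c = 40%: 0.40 + 0.60 × 0.44 = 66.4%, a gain of 22.4 points.

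**5. Would requiring CR at two visits cure it?** Assuming independent misses and lasting clearance, the no-effect rate becomes c + (1 − c) × m². With f = 0 and m = 0.10 it falls from 10% to 1%. The last three rows of the table fall only from 19.0% to 10.9%, 28.0% to 20.8% and 52.0% to 42.4%. A second look removes most of the sampling part and leaves the fulguration part, so it does not replace a split by fulguration status.

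**The case against.** The strongest reply is that the size is unknown and the comparator unspecified. Both statements are correct. Fulguration is optional and mentioned in only one screening branch; q also requires clearance to last through 3 months of treatment plus up to 12 weeks of screening. Section 6.2.4.2 names no series. Only the phase 2 study is described as enrolling residual CIS, and its description does not say fulguration was barred. The phase 1 result (29% of 17 Tis subjects) and the phase 3 update (39% to 40% at 3 months) are also available, with no residual-CIS rule stated in the text provided. Section 2.2 calls the procedure standard of care, so some historical patients may have had it too.

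A reader might also infer that the lack of a confirming biopsy biases the comparison. The documents do not show that: the phase 1, 2 and 3 summaries describe no confirmation step either, so a single reading may affect both sides alike. The 6- and 12-month rates and recurrence-free survival already add later looks. The documented differences from phase 2 are the entry rule and its requirement of negative cytology and no histological disease of any kind.

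Part of the data may already exist, since section 2.2 collects surgical history and dated prior treatments. Splitting a small CIS group also gives little precision: 3/6 has an exact 95% interval of 12% to 88%.

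What survives is that the plan permits ablation, requires no residual CIS afterwards, pools the two groups and foresees a historical comparison without matching entry rules.

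**Conclusion.** The point holds as a possible upward bias of undetermined size. Its direction follows from the text, provided the comparator's CIS had not been ablated. Its magnitude rests entirely on assumed f, q and m: 0% to about 52% for CR with no drug effect, and 0 to about 22 points of apparent gain over 44%.

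Two stronger readings are not supported. One is that an inactive treatment would show a sizeable CR rate. With rare fulguration and few missed lesions the no-effect rate is near zero, and the documents do not say how common either is. The other is that the interim result of 5/12 (41.7%, given as 40% in section 1.2.3) is explained by this mechanism. That section does not say how many of the 12 had CIS, so the figure cannot be set against a CIS-only rate.

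Severity is low to moderate. CR is a secondary endpoint reported descriptively, and the primary safety endpoint is untouched.

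**What to change.** In sections 6.2.4.2 and 10.4.3:

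1. Record from the operative note whether CIS was fulgurated or resected between the qualifying specimen and the first dose.
2. Report CR with its 95% confidence interval overall and, descriptively, by that status. Note this in 10.4.7, which now excludes subgroup analyses.
3. Make any historical comparison like with like: patients with non-fulgurated (residual) CIS against series that enrolled residual CIS. Where that cannot be done, state beside the comparison that the entry rules differ.
4. Optionally, add a supplementary row for CR present at both 3 and 6 months among patients assessed at both. It should not become the main activity result: it is less comparable with the historical 3-month rates, and biopsy at each visit is discretionary under 6.2.3.

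Items 1 to 3 leave the pre-treatment procedure as it is and add no patient visit or biopsy. The cost is one CRF item and a few table rows. The downside is small denominators and wide intervals, so the split shows how far the pooled rate depends on ablated patients and cannot support a formal contrast. If fulguration was rare, the table will show that and the concern falls away.

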### **2.3 PARTICIPANT REGISTRATION AND STATUS UPDATE PROCEDURES**

Registration and status updates (e.g. when a participant is taken off protocol therapy and when a participant is taken off-study) will take place per CCR SOP ADCR-2, CCR Participant Registration & Status Updates found at: [https://nih.sharepoint.com/sites/NCI-CCR-OCD-Communications/SitePages/OEC-Administrative---Clinical-Research-\(ADCR\).aspx?Mode=Edit](https://nih.sharepoint.com/sites/NCI-CCR-OCD-Communications/SitePages/OEC-Administrative---Clinical-Research-(ADCR).aspx?Mode=Edit).

### 2.3.1 Treatment Assignment Procedures

#### Cohorts

Number	Name	Description
1	Run in Cohort	Subjects with high grade non-muscle invasive urothelial (transitional cell carcinoma) of the bladder. Up to 12 subjects
2	Expansion Cohort	Subjects with high grade non-muscle invasive urothelial (transitional cell carcinoma) of the bladder. Up to 24 subjects enrolled after the run in cohort is filled.

#### Arms

Number	Name	Description
1	Run In	Durvalumab + Vicineum, escalating doses. Up to 2 dose levels will be evaluated in the first 6 – 12 subjects
2	Expansion	Durvalumab + Vicineum, at the MTD. Up to 24 subjects

Subjects in cohort 1 will be directly assigned to arm 1. Subjects in cohort 2 will be directly assigned to arm 2.

### 2.4 BASELINE EVALUATION

See section [3.4](#), Study Calendar.

#### 2.4.1 Baseline studies

Performed within 7 days before starting treatment. If Clinical evaluation laboratory work was also performed within 7 days before starting treatment, then those values can be used for baseline evaluation.

- Hematology (Complete blood count plus differential and platelet count)
- Acute care panel (Na+, K+, Cl, CO2, glucose, BUN, creatinine)
- LDH
- Pre-albumin
- Pancreatic enzymes (amylase, lipase)
- Hepatic panel (alkaline phosphatase, ALT, AST, total bilirubin)
- Mineral panel (albumin, calcium, magnesium, phosphorus)
- Thyroid function tests

#### 2.4.2 Urine studies (within 7 days prior to initiation of study therapy)

- Urine cytology
- Urinalysis

- Urine culture and sensitivity

#### **2.4.3 Research Assessments at Baseline (within 7 days prior to initiation of study therapy)**

Please refer to section [5.2](#).

#### **2.4.4 Other Assessments**

- Weight
- Physical Exam, ECOG status, and medications

### **3 STUDY IMPLEMENTATION**

This is a single arm study. A run in cohort of up to 12 evaluable subjects and an expansion cohort of up to 24 evaluable will be evaluated. No randomization or stratification will be performed.

#### **3.1 STUDY DESIGN**

See [SCHEMA](#).

##### **3.1.1 Dose Limiting Toxicity (DLT)**

A DLT will be defined as any Grade 3 or higher toxicity that occurs during the initial 6-week period the subject is on treatment (i.e., the DLT evaluation period). Toxicity that is clearly and directly related to the primary disease or to another etiology is excluded from this definition. Since this trial also involves immunotherapy, immune-related AEs (irAEs) are defined as AEs of an immune nature (i.e. inflammatory) in the absence of a clear alternative etiology. In the absence of a clinically significant abnormality, repeat laboratory testing will be conducted to confirm significant laboratory findings prior to designation as a DLT. The following will be DLTs:

- Inability to reduce prednisone dose below 10 mg within 6 weeks (rather than 12 weeks) due to ongoing immune-related adverse reaction of Grade >1
- Any Grade 4 irAE not attributed to local tumor response (e.g., inflammatory reaction attributed to local tumor response or inflammatory reaction at sites of metastatic disease or lymph nodes)
- Any  $\geq$  Grade 3 colitis
- Any Grade encephalopathy
- Any  $\geq$  Grade 3 neurotoxicity
- Any  $\geq$  Grade 3 peripheral neuromotor syndromes
- Any Grade 2 or higher noninfectious pneumonitis irrespective of duration
- Any Grade 3 irAE, excluding colitis that does not downgrade to Grade 2 within 3 days after onset of the event despite optimal medical management including systemic corticosteroids or does not downgrade to  $\leq$  Grade 1 or baseline within 14 days

- Total bilirubin  $>1.5 - 3.0 \times$  ULN (Grade 2 Hyperbilirubinemia)
- ALT or AST  $>8 \times$  ULN
- ALT or AST  $>5 \times$  ULN for more than 2 weeks
- ALT or AST  $>3 \times$  ULN and
- ALT or AST  $>3 \times$  ULN and INR  $>1.5$
- ALT or AST  $>3 \times$  ULN with appearance of fatigue, nausea, vomiting, right upper quadrant pain or tenderness, fever, rash, and/or eosinophilia ( $>5\%$ )
- Any Grade  $\geq 3$  non-irAE toxicity that does not downgrade to Grade  $\leq 1$  or baseline status (for patients who entered the study with an existing laboratory abnormality) within 14 days
- Inability to receive  $\geq 75\%$  or more of scheduled study treatment (both Vicineum and durvalumab) during the first six weeks of the trial
- Persistent Grade 2 events possibly related to study drugs such as persistent nausea, vomiting, diarrhea, or fatigue that are refractory to maximal intervention or are severely limiting to the patient's ability to carry out activities of daily living.

The definition excludes the following conditions:

- Grade 3 endocrine disorder (thyroid, pituitary, and/or adrenal insufficiency) that is managed with or without systemic corticosteroid therapy and/or hormone replacement therapy and the subject is asymptomatic
- Concurrent vitiligo or alopecia of any AE grade
- Grade 3 infusion-related reaction (first occurrence and in the absence of steroid prophylaxis) that resolves within 6 hours with appropriate clinical management
- Isolated Grade 3 electrolyte abnormalities that are not associated with clinical signs or symptoms and are reversed with appropriate maximal medical intervention within 3 days.
- Grade 3 inflammatory reaction attributed to a local antitumor response (e.g., inflammatory reaction at sites of metastatic disease, lymph nodes, etc.)

